13.2 Discontinuation and Withdrawal of Subjects

Subjects may withdraw voluntarily from the study at any time. They may be withdrawn from the study by the Investigator if:

- A serious adverse event (SAE) occurs.
- The Investigator believes that for safety reasons it is in the best interest of the subject to be withdrawn.
- The subject withdraws consent.
- A positive urine drug screen at any visit.
- A positive pregnancy test at any visit; the subject reports pregnancy.
- Inability to locate and quantify a motor threshold as defined in the protocol or a motor threshold above 1.6 SMT.
- Investigator sets a treatment goal below 120% of MT.

Discontinuation information [e.g., date and the reason(s) for discontinuation] must be recorded in the subject's CRF (i.e., Study Termination Record page).

Follow-up information will be obtained for subjects who experience an SAE.

Subjects withdrawn from the study will not be replaced.

13.3 Compensation

As an incentive to complete the study and compensation for their time and effort, participants will be offered a \$50 stipend if they complete all study treatment visits or discontinue due to intolerance of treatment.

14 DEVICE DESCRIPTION AND RTMS ADMINISTRATION

14.1 Device Description

The NeuroStar TMS Therapy System is a computerized electromechanical instrument that produces and delivers brief duration, rapidly alternating (pulsed) magnetic fields to induce electrical currents in localized regions of the cerebral cortex. The NeuroStar TMS Therapy System is offered in the following configurations:

[figure not shown]
- Single mobile console configuration: mobile console, rTMS stimulation coil, head support system, chair, and TMS TrakStar practice data management system.

- Multiple mobile consoles/TMS TrakStar system configurations to address the needs of facilities with large subject populations.

During TMS, the conductive substance of interest is the brain, in particular the region of the cortex that lies beneath the NeuroStar TMS Therapy System treatment coil. This is the NeuroStar TMS Therapy System component that rests against the subject's head and transmits magnetic pulses to the subject's brain. The induced current is tangential to the scalp at the cortical surface and diminishes in magnitude with increasing depth.

For further detailed description on the NeuroStar TMS Therapy System, see the User Manual.

14.2 Subject Flow

Escalation Protocol to achieve prescribed % MT

- Begin at 90%MT
- Decrease at any time for intolerance by 10%
- Every 3:45 minutes Increase or Decrease by 10%
- Increase to patient tolerance; goal of 120% MT

Patient Reported Outcomes:

- Comfort/Pain Scale
- Depression Scale PHQ-9
- Patient Treatment Preference
- AE's

15 MEASURES TO AVOID STUDY BIAS

15.1 Subject Identification

Each subject will be assigned a unique screening number after signing the study consent. This number will consist of an assigned unique, 3-digit subject identifier. For example, the first subject screened would be subject 001.

Subjects should be identified to the Sponsor only by their assigned number, age and sex. The Investigator must maintain a master list linking subject names and the identifying information indicated above.

15.2 Randomization

A randomization schedule will be generated by Neuronetics or a designated contract research organization (CRO). Eligible subjects will be randomly assigned to the Dash treatment protocol (Y) or Dash with the SoftStart feature enabled (X). Randomization numbers will be recorded in the screening log and on the subject's CRF. Randomization numbers may not be reassigned.

15.3 Blinding

Subjects will be blinded to all treatments. Subjects will be randomized to begin with either treatment X or treatment Y. Treaters and Clinicians will be aware of the treatment protocol assignments once assigned to subjects. Treaters will administer the Comfort scale but will not score the scales. Subjects will not be able to view previous responses to the Comfort, Preference or Depression questionnaires. Treater scripts will be used to administer the TMS changes and subject questionnaires.

15.4 Treatment Consistency

The same treater and same TMS treatment unit will be utilized for each subject whenever possible over the course of the study treatments.

16 COMFORT EVALUATIONS

Primary endpoint: The difference in the change in VAS scores for Comfort after rTMS stimulation between treatments administered with the Dash protocol and treatments administered with the Dash protocol with SoftStart feature enabled. Comfort will be evaluated as a change for all observations between groups, observations from Baseline to end of escalation phase, observations between groups during the crossover phase and observations

within a patient between treatments in the cross-over phase. Comfort will also be analyzed over time and by number of treatments between groups. See also section 18.

In the event that adverse events occur, those data will be summarized using standard descriptive statistics (frequency distributions, percentages, listings).

17 SAFETY EVALUATIONS

A medical history will be obtained at the screening visit including a list of medications and history contraindicated for TMS therapy and this protocol.

All spontaneous adverse events, serious or non-serious will be recorded during and after the rTMS stimulation procedures. Serious Adverse Events will be reported to Neuronetics by the study center within one business day of notification. Neuronetics will report any and all SAEs and other safety events, as applicable, to the IRB and/or the FDA within the pre-specified timeframes, as applicable.

17.1 Adverse Event Definitions

An *adverse event* is any untoward, undesired, or unplanned event in the form of signs, symptoms, disease, or laboratory or physiological observations occurring in a person who has received rTMS stimulation with a Neuronetics device or in a Neuronetics clinical study. The event need not be causally related to the Neuronetics device or Neuronetics clinical trial. An AE includes, but is not limited to:

- Any clinically significant worsening of a pre-existing condition.
- An AE occurring from overdose (i.e., a dose higher than that described in the protocol) of a Neuronetics device, whether accidental or intentional.
- An AE occurring from abuse (e.g., use for non-clinical reasons) of a Neuronetics device.
- An AE that has been associated with the discontinuation of the use of a Neuronetics device;

A *preexisting condition* is a clinical condition (including a condition being treated) that is diagnosed before an informed consent form is signed and is documented as part of the subject's medical history.

A *serious adverse event* (SAE) is defined by Neuronetics as an AE that:

- Results in death:
- Is life threatening (see below).
- Requires inpatient hospitalization or prolongation of an existing hospitalization.

- Results in permanent impairment of a body function or permanent damage to a body structure.
- Necessitates medical or surgical intervention to preclude such impairment.
- Results in a congenital anomaly or birth defect.

Additionally, *important medical events* that may not result in death, be life-threatening, or require hospitalization, may be considered SAEs, based upon appropriate medical judgment.

Life threatening refers to immediate risk of death as the event occurred per the reporter. A life-threatening event does not include an event that, had it occurred in a more severe form, might have caused death, but as it actually occurred, did not create an immediate risk of death.

Hospitalization is to be considered only as an overnight admission. Hospitalization or prolongation of a hospitalization constitutes an AE to be classified as serious.

Note that hospitalizations planned before the start of the study, for a preexisting condition that has not worsened, do not constitute an SAE (e.g., elective hospitalization for a total knee replacement due to a preexisting condition of osteoarthritis of the knee that has not worsened during the study).

Anticipated adverse events:

Anticipated events such as Headache, Dizziness, and Ear popping do not need to be recorded unless they are higher in frequency, severity, or duration than considered normal for TMS therapy. For this study, these events should be noted on the patient treatment form in the comments area.

Adverse Events of Special Interest:

An adverse event of special interest is a device-specific adverse event designated by Neuronetics to be reported in the same time frame as an SAE, even if it does not meet serious reporting criteria. For this protocol, seizure should be reported as an adverse event of special interest.

If there is any doubt whether the information constitutes an SAE, the information should be treated as an SAE for the purpose of this study.

Definition of Severity

The seriousness and severity must be evaluated independently when documenting the AEs in the records. There are three definitions of AE severity:

Mild: Awareness of sign or symptom, but easily tolerated

Moderate: Discomfort enough to cause interference with usual activity

Severe: Incapacitating with inability to work or do usual activity

Determining the Relationship: (if any) Between an Adverse Event and the Study Device:

Not related: The AE is unlikely to have been caused by study device.

Possibly related: It is unclear whether the AE may have been caused by study device.

Related: The AE is likely to or definitely have been caused by study device.

When assessing the relationship between an investigational product/protocol and an AE, the following parameters are considered:

- Temporal relationship between the investigational device/protocol and the AE
- Biologic plausibility of relationship
- Subjects' underlying clinical state or concomitant agents/therapies
- Where applicable, whether the AE abates on discontinuation of the investigational device (dechallenge)

SAEs that are not device-related may nevertheless be considered by the participating Investigator or Neuronetics Medical Affairs to be related to the conduct of the clinical study, i.e., to a subject's participation in the study.

17.2 Timing for Reporting of Serious Adverse Events

Any SAE (as defined above) regardless of causal relationship, must be reported immediately to Neuronetics Medical Affairs (within one business day) by emailing to Neuronetics a completed serious adverse event form to [contact] and then confirming by [contact]) that the email was received. If no direct phone contact is made, the investigator should repeat attempts to notify Neuronetics Inc. or designated representative until receipt is acknowledged. The SAE may be reported using IRB required forms, or Neuronetics forms 25-44028-000, Serious Adverse Event Form, or 25-80031-000, Medical Event Form. Compliance with this time requirement is essential so that Neuronetics may comply with its regulatory obligations.

Follow-up information relating to an SAE must also be reported to Neuronetics Medical Affairs within one (1) business day after the information is received. The patient should be observed and monitored carefully until the condition resolves or stabilizes or its cause is identified. Any emergency must be reported to the Neuronetics Medical Affairs immediately (within one business day).

For all other inquiries and information about this study, contact the Clinical Operations representative identified in Section 1.1 of this protocol.

17.3 Reportable Events

All AEs and SAEs, regardless of relationship to the protocol or rTMS device, that are collected during the rTMS stimulation procedure will be recorded on source documents and recorded on the subject's CRFs. Neuronetics will instruct the Investigator to follow all AEs, SAEs, and other reportable events until the event has subsided or values have returned to baseline, or in case of permanent impairment, until the condition stabilizes.

The Investigator will provide all documentation pertaining to an SAE (e.g., additional laboratory tests, consultation reports, discharge summaries, postmortem reports, etc.) to the medical monitor in a timely manner. Reports relative to the subject's subsequent course must be submitted to the Sponsor until the event has subsided or, in case of permanent impairment, until the condition stabilizes.

Other information reportable to Neuronetics, while not meeting the definition of an AE, is reportable to Neuronetics with the timeliness of an SAE. This includes:

- Pregnancy occurring during the study period in which the subject was exposed to the rTMS device.
- Overdose (e.g., a dose higher than that prescribed by a healthcare professional for clinical reasons) with or without AEs.
- Abuse (e.g., use for non-clinical reasons) with or without an AE.
- Inadvertent or accidental exposure with or without an AE.
- Device malfunction that would likely result in death, serious injury or other significant adverse event.

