9 CLINICAL SECTION

9.1 Introduction TMS and SoftStart

Repetitive transcranial magnetic stimulation (rTMS) is defined as the administration of a series of magnetic stimuli to the brain for the purpose of altering brain function. NeuroStar transcranial magnetic stimulation (TMS) Therapy was FDA cleared in 2008 for the treatment of major depressive disorder in adult patients who have not received benefit from prior medication. This procedure is non-invasive, does not require anesthesia, and may be delivered in an appropriately staffed outpatient setting. Although generally regarded as safe and without lasting adverse effects, patients treated with rTMS may experience minor side effects. The most common side effects are discomfort due to stimulation of the scalp musculature under the site of stimulation and muscle tension headaches which may persist for 1-2 hours post stimulation.^{8,9} These effects are thought to be due to the direct activation of muscles and nerves near the stimulating coil and both duration and intensity of stimulation impact the incidence of these effects.

Stimulus intensity is based on individually determined resting motor threshold (RMT or MT, minimum intensity to elicit muscle twitches at relaxed upper or lower extremities, by visual inspection or electromyography). The recommended stimulation intensity range is 110-120% MT.²¹ According to the original NeuroStar protocol, after determining the MT, a treatment session included stimulation at 120% motor threshold with a pulse sequence of 10 Hz for 4 seconds, followed by a 26 second inter-train interval (quiet period). A session lasted for a total of 37.5 minutes with a total of 3,000 pulses. A full NeuroStar treatment includes 30 daily sessions over 6 weeks with an additional 6 session ramp down over 3 weeks for a total of 9 weeks.¹⁵ In clinical practice, during the first 5-10 treatment sessions clinicians typically “ramp up” patients to the prescribed treatment intensity (% MT) to minimize side effects. Treatment sessions often start at 80-90% MT and stimulation intensity is increased to the prescribed level based on individual patient tolerance.

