If the subject reaches the prescribed %MT at any of these visits and sustains that MT through the final 3:45 minute time interval, the next study visit will be the start of the crossover phase of the study (Crossover Treatment 1). If the subject does not achieve the prescribed MT by the end of the 5th Treatment session, they will continue to Crossover Treatment 1 at the next visit, however, attempts to achieve the prescribed %MT should continue and be documented.

Crossover Phase

Visit 1

Subjects will be crossed over to the alternative treatment protocol, those who had received treatment X will then receive treatment Y and vice versa. Subjects will start treatment at the %MT established in the previous session and all study treatment assessments completed on Treatment Visits 2-5 of the Ramp Phase will be repeated and documented for each visit of the Crossover Phase.

Visits 2-4

Subjects will be crossed over to the alternative treatment protocol, those who had received treatment X will then receive treatment Y and vice versa. At the start of treatment, subjects will start treatment at the %MT established in the previous session and all study treatment assessments completed on Crossover visit 1 will be repeated.

Visit 4: Final Crossover Visit

At the start of treatment for Crossover visit 4, subjects will be crossed over to the alternative treatment protocol, subjects will start treatment at the %MT established in the previous treatment and all study treatment assessments completed on Crossover visit 1 will be repeated.

At the end of the final treatment, the treatment protocol for further TMS sessions will be determined by the clinician and the patient as part of their normal care. The treatment choice will be documented, and the subject will be exited from the study. See subject flow diagram in section 14.2 for additional information.

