17.4 Reporting Procedures

All AEs collected during stimulation visits will be recorded in the adverse event record of the subject's CRF. The information recorded should be based on the signs or symptoms detected during the physical examination and clinical evaluation of the subject. Signs and symptoms should be recorded using standard medical terminology.

The following AE information must be included (when applicable): the specific condition or event and direction of change; whether the condition was preexisting (i.e., an acute condition present at the start of the study or history of a chronic condition) and, if so, whether it has worsened (e.g., in severity and/or frequency); the dates and times of occurrence; duration; severity; causal relationship to the product under study ; action taken; and outcome.

IRB Reporting:

Any AE's/SAE's should also be reported in writing to the reviewing IRB, per their requirements.

MDR Reporting:

As the study device is commercially available, all adverse events also need to be reported through FDA's MDR reporting system. <https://www.accessdata.fda.gov/scripts/medwatch/>

Follow-up of Adverse Events

All AEs recorded during the study are to be followed in accordance with good medical practice until they are:

- resolved, stabilized, or judged no longer clinically significant, or
- if a chronic condition, until fully characterized, or
- for 30 days, which may extend through the follow-up phase for treatment related AEs or SAEs that occur or are ongoing at the last treatment session.

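### The adverse event recording rules disagree on window and scope, state no end of collection, and schedule no contact after a subject's last study session

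*Protocol*

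**What the plan says.** The protocol describes AE recording in several places.

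- **Section 17**: "All spontaneous adverse events, serious or non-serious will be recorded during and after the rTMS stimulation procedures".
- **Section 17.3**: AEs and SAEs, whatever their relationship to the device, "that are collected during the rTMS stimulation procedure will be recorded on source documents" and on the CRF.
- **Section 17.4**: "All AEs collected during stimulation visits will be recorded in the adverse event record of the subject's CRF".
- **Section 17.1, on expected symptoms**: "Anticipated events such as Headache, Dizziness, and Ear popping do not need to be recorded unless they are higher in frequency, severity, or duration". The comparison is with what is usual for TMS, and these events go in the comments area of the treatment form.
- **Section 17.2**: any SAE is reported within one business day. No last onset date is given.

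On the end of the study, section 13.1 says of the final crossover visit: "The treatment choice will be documented, and the subject will be exited from the study". In the schedules (protocol section 8 and SAP Appendix A), the last AE mark and the study exit mark are in the same column.

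For withdrawn subjects, section 13.2 requires the date and reason, and adds: "Follow-up information will be obtained for subjects who experience an SAE". Section 17.4 follows recorded AEs to resolution or stabilisation, or "for 30 days, which may extend through the follow-up phase for treatment related AEs or SAEs" present at the last session. Neither schedule contains a follow-up phase.

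SAP section 6.6.1 makes a descriptive comparison of AE incidence, severity and frequency between groups the primary safety endpoint. SAP section 6.7 computes AE rates over an *analysis interval* that the SAP does not define.

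**The concern.** Staff who follow section 17.3 literally and staff who follow section 17 would build different AE datasets from the same subjects. Because of the section 17.1 exemption, the same symptom may be a CRF record for one subject and a free-text comment for another. That choice depends on a threshold the protocol does not define. The treaters and clinicians who would have to apply it know the treatment (section 15.3).

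The end of the study adds a second gap. After an intermediate session, the next visit gives an occasion to learn of anything that arose in between. After the last session there is no such occasion. The same holds for a subject who stops early because of discomfort. Discontinuation for that reason is a secondary outcome, so those sessions bear on the study question.

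At stake is whether the AE table by treatment, which is the SAP's primary safety endpoint, has a defined content. The comfort endpoint is not affected.

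**Working it through.** The plan gives no figure to reproduce here. The check compares the rules and then counts sessions.

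**1. The rules side by side**

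| Protocol section | Events covered | When | End stated |
|---|---|---|---|
| 17 | all spontaneous AEs | in and after the procedures | no |
| 17.3 | all AEs and SAEs | collected in the stimulation procedure | no |
| 17.4 | all AEs | collected at stimulation visits | no |
| 17.1 | exempts headache, dizziness, ear popping unless beyond normal | not stated | no |
| 17.2 | SAEs | any | no |

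Take a hypothetical non-serious event outside the section 17.1 exemption. It starts an hour after a session and is mentioned at the next visit. Sections 17 and 17.4 both record it. Section 17.3, read literally, does so only if it is collected in the course of stimulation.

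Now let the same event follow the final session. Section 17 would still record it if someone reported it, but there is no further study visit at which to ask. If the event were a headache of ordinary intensity, section 17.1 would keep it out of the AE record under any of the three windows.

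**2. Sessions with no later study visit**

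Inputs: 1 to 5 ramp sessions (section 13.1), 4 crossover sessions (both schedules), and 40 subjects, 20 per starting treatment (section 12.1 and synopsis). With r ramp sessions a completer has r + 4 sessions, and only the last has no later visit. The share is 1/(r + 4).

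| r | sessions | share without a later visit |
|---|---|---|
| 1 | 5 | 1/5 = 20.0% |
| 2 | 6 | 1/6 = 16.7% |
| 3 | 7 | 1/7 = 14.3% |
| 4 | 8 | 1/8 = 12.5% |
| 5 | 9 | 1/9 = 11.1% |

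If all 40 complete:
- whole study: from 40/(40 × 5) = 40/200 = 20% to 40/(40 × 9) = 40/360 = 11.1%;
- crossover phase: 40/(40 × 4) = 40/160 = 25%.

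**3. Balance between treatments**

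Let A be the first-assigned treatment and B the other. The order is A (r times), then B, A, B, A, so the final session is always on A. With 20 subjects starting on each treatment, 20 of the 40 final sessions are on X and 20 on Y.

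Within a subject, the sessions that do have a later visit number r + 1 on A (2 to 6) and 2 on B.

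For early stoppers, the treatment given at the last session is not fixed by design. The documents give no expected dropout by treatment, so any imbalance there cannot be sized.

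**The case against.** The strongest reply is that the plan is less closed than section 17.3 suggests. Section 17 explicitly reaches past the procedure. Section 17.4 can be read as saying where events are collected, not when they began, so an overnight event told at the next visit fits it. AEs are marked at every treatment visit, SAE reporting has no cut-off, and AEs occurring or ongoing at the last session are followed. The AE comparison is descriptive, in an exploratory study whose sample size is not based on power.

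Much of this stands and limits the point. A reader might infer that AE collection closes with the last session and that later events are lost. The documents do not support that: the window is contradictory and open-ended, and spontaneous reports remain possible. What the reply does not supply is a scheduled occasion to ask. Section 17 creates none, and the follow-up rule in 17.4 concerns events already recorded.

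A reader might also cite section 9.1, which mentions "muscle tension headaches which may persist for 1-2 hours post stimulation", as proof that headaches are missed after the last session. It is weak support. The sentence is about how long headaches last, not when they begin, and the section 17.1 exemption would exclude an ordinary one anyway.

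Nor are the follow-up rules in 13.2, 17.3 and 17.4 in serious conflict. Section 13.2 does not say that only SAEs are followed, and the other two are broadly compatible. The real defect there is the reference to a follow-up phase that the schedules lack.

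**Conclusion.** The point holds in a limited form. The recording rules are inconsistent in window and in scope, and no end of collection is stated. Non-serious events that start after the last session, or after a discomfort-driven stop, have no scheduled contact to collect them. The size is one session per completer: 40 of 160 crossover sessions, or 11.1% to 20.0% of all sessions, assuming no dropout and four crossover sessions each.

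Two further inferences are tempting but unsupported.

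- **Bias against one treatment.** Counting the crossover phase alone, the first-assigned treatment has one session with a later visit and the other has two. The ramp sessions reverse this within a subject, and the final sessions split 20/20 between X and Y. SAP section 6.7 does not restrict the AE analysis to the crossover phase. Imbalance is possible only through early stoppers, and the documents do not say how large it could be.
- **A count of missed events.** The documents give no rate of events arising after a session, and nothing in them shows that such events are those most likely to differ between the treatments.

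The correction is worth making because it is cheap and gives the primary safety endpoint a defined content. It does not call the design into question.

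**What to change.** 1. Reconcile protocol sections 17, 17.1, 17.3 and 17.4 into one recording rule. It should cover onsets both in and after a session and name the end of AE collection.
2. Capture the anticipated events of section 17.1 in a structured field, so that they can be tabulated by treatment. Correcting the window alone would leave ordinary headache, dizziness and ear popping in free text.
3. Ask the same scripted AE question, about the time since the last session, at every treatment visit. Ask it once more, before treatment, at the next routine TMS visit after Crossover visit 4 or after early study discontinuation, and by phone if TMS has stopped. Asking before treatment keeps the answer tied to the last study session. Add this contact to both schedules.
4. Define the analysis interval in SAP section 6.7 to match the rule.
5. Remove the follow-up phase from section 17.4, or define it.

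The cost is a minor amendment, one CRF field and one question. Study exit moves by about one day, with a phone call for those who leave TMS. For most subjects the extra contact should be a visit that already takes place. Section 9.1 describes 30 daily sessions in a full course; if that applies here, 30 − 9 = 21 to 30 − 5 = 25 remain after the study sessions.
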